#### **4.8. Exploration of Exposure - Safety Parameters**

Based on the clinical relevance, the AE data for gastrointestinal disorders will be dichotomized into presence or absence of an AE grade  $\geq 3$  at any visit postdose up to the last treatment day, while for pruritus and specific subclasses of gastrointestinal AE's (e.g. diarrhea, constipation, abdominal pain) dichotomization will be based on any occurrence at any visit postdose up to the last treatment day (Day 22 to Day 64). JNJ-67953964 exposure metrics will be classified into 3 or 4 categories dependent on the number of subjects per quantile. Similarly, an additional category will be included for the placebo-randomized subjects; in this case the exposure metrics will be assigned to a value of zero. Exploratory bar plots of number of subjects with an AE versus exposure groups will be generated for the AE's of interest pruritis and GI complaints. If appropriate additional plots may be generated for other AE's with at least one observation of grade 3 or higher. If appropriate, a logistic regression may be used to describe the relationship between exposure and the occurrence of an AE. The exposure metrics to be used in the PK-safety evaluation will be  $C_{max}$  (see Section 4.5). Additional exposure metrics may be tested if the  $R^2$  of the correlation between PK parameters is less than 0.8.

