The treatment phase of the trial will consist of 3 periods. A placebo lead-in period of concealed duration, after which subjects will enter the double-blind treatment period when they will be randomly assigned to 10 mg JNJ-67953964 or continue placebo for 6 weeks. Subjects who complete the treatment period, will then enter the withdrawal period and be treated with placebo for the remaining time of the treatment phase of the study. The total study duration for each subject will be approximately 16 weeks. There will be 11 scheduled visits to the clinical research center including screening during the study. An overall flow diagram of the study is shown in Figure 2:

Figure 2: Flow diagram of the study

Eligibility Screening Examination

After giving written informed consent, subjects will be screened within 35 to 2 days prior to Day 1 to ascertain their eligibility for the study per the inclusion and exclusion criteria. Upon completion of all informed consent form (ICF) procedures, recording of AEs and concomitant medication will start.

The symptoms of depression will be assessed using the (structured interview guide for the) MADRS.

Double-blind Treatment Phase

The duration of the double-blind treatment phase will be 11 weeks divided into 3 periods. Subjects will visit the study center for baseline visits on Day 1. The subject will receive study medication after completion of the visit on Day 1. The first dose will be taken at home on Day 2.

Medication will be dispensed at each study visit during this double-blind period. All study medication will be taken in fasting condition.

During the double-blind study phase, the subjects will visit the study center for out-patient visits every 1-2 weeks as indicated in the TES.

Lead-in period

Subjects who successfully complete the baseline examination visit at the clinical site/unit, will be treated with placebo for the entire duration of the lead-in period. Investigators and subjects will be blinded to the exact duration of lead-in period for each subject in the study.

Treatment period

At the end of the lead-in period both placebo lead-in responders and placebo lead-in non-responders will be randomized to receive either placebo or 10 mg JNJ-67953964 in a 1:1 ratio for 6 weeks. Investigators and subjects will remain blinded to exact timing of the randomization, response criterion and study drug treatment assignment for each subject.

Withdrawal period

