**Table 2: Overview of Trials to be Included in the Exposure-Response Analysis**

Study No.	Study Title & Design	Brief Description of Exposure and Response Data
67953964MDD2001	
Title: A Phase 2a Randomized, Double-blind, Placebo-Controlled, Parallel-Group, Multi-center Study Investigating the Efficacy, Safety, Tolerability and Pharmacokinetics of JNJ-67953964 in Subjects with Major Depressive Disorder.
 
Design: The treatment phase of the trial will consist of 3 periods. A placebo lead-in period of concealed duration, after which subjects will enter the double-blind treatment period when they will be randomly assigned to 10 mg JNJ-67953964 q.d. or continue placebo in a 1:1 ratio for 6 weeks. Subjects who complete the treatment period, will then enter the withdrawal period and be treated with placebo for the remaining time of the treatment phase of the study.
	
No. of subjects with Exposure data available/total no. in study : 71/142 (Planned)
 
Exposure metrics derived from popPK on Day 22, 29, 43, 50, 57 (Trt Week 0, 1, 3, 4, 5 and 6) and 78 (EOS).
 
No. of subjects with MADRS and SHAPS data available/total no. in study : 142/142 (Planned)
 
MADRS and SHAPS assessment at Screening (Week -5 to 0) and on Day 1, 8, 15 (Lead-in Week 0, 1, 2), 22, 29, 43, 50, 57 (Trt Week 0, 1, 3, 4, 5 and 6) and Day 78 (EOS).
 
Safety assessments: All AEs and special reporting situations, whether serious or non-serious, will be reported from the time a signed and dated ICF is obtained until completion of the participant's last study-related procedure, which may include contact for follow-up of safety.

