6. **MADRS and SHAPS PK/PD Modelling:** The change from baseline MADRS and SHAPS total score will be modelled separately using specific parameters for placebo effect, and drug effect, using individual JNJ-67953964 exposure estimates in the drug effect sub-model. Baseline scores, co-medication, gender, race and age at baseline will be tested as potential covariates. Primary analysis on MADRS will be performed on the enriched population (lead-in non-responders). In case no effect on MADRS is found, change from baseline SHAPS total scores will be analyzed on the full dataset. If appropriate, the analysis on MADRS may be repeated on the full dataset, where both lead-in placebo response as well as baseline SHAPS total score will be tested as covariate in the model;
7. **Simulations of change in MADRS and SHAPS:** Based on the final PK/PD model (including covariates, if any), model based simulations of the drug effect on MADRS and SHAPS change from baseline (i.e. net MADRS/SHAPS change from baseline after correction for placebo response) will be generated;

8. **Exploration of Exposure versus Safety Parameters:** Exploratory bar plots of AE grade versus exposure quantiles will be generated for the AE's of interest: pruritis and GI complaints. Other AE's with one or more observations of grade 3 or higher may be included in the exploratory analysis as well. If appropriate, a logistic regression may be used to describe the relationship between exposure and the occurrence of an AE.
9. **Reporting:** Prepare the report in accordance with the FDA and EU guidance on population PK.

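### The exposure-safety bar plots in SAP 4.8 show counts, not proportions, beside a placebo category 3 to 4 times the size of each drug group, so a doubled AE risk on drug can look like fewer events than on placebo

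*SAP*

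**What the plan says.** SAP 4.8 builds the figure in three steps.

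- Drug exposure is grouped: "JNJ-67953964 exposure metrics will be classified into 3 or 4 categories dependent on the number of subjects per quantile".
- Placebo is added undivided: "an additional category will be included for the placebo-randomized subjects; in this case the exposure metrics will be assigned to a value of zero".
- The plotted quantity is a count: "Exploratory bar plots of number of subjects with an AE versus exposure groups will be generated", for pruritus and GI complaints.

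The section names no percentage, proportion or group size for this plot. It allows a logistic regression of AE occurrence on exposure, but only if judged appropriate.

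Step 8 of SAP 4.2 describes the display differently: "Exploratory bar plots of AE grade versus exposure quantiles will be generated". It gives no denominator either.

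Protocol 4.1 fixes the allocation: subjects are "randomized to receive either placebo or 10 mg JNJ-67953964 in a 1:1 ratio for 6 weeks". SAP Table 2 plans exposure data for 71 of 142 subjects. Protocol 9.5 provides, for each AE, the percentage of subjects affected by treatment group.

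**The concern.** A count bar can be compared with another only if the two groups are of similar size. The drug quantiles meet that condition. The placebo category does not, yet it is in the plot as the zero-exposure reference, so readers will compare the drug bars with it.

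With counts, an AE unrelated to drug tends to show a drop from placebo to every exposure group. A moderate excess on drug can show as no difference or as a deficit.

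Relating exposure to pre-defined safety parameters is one of the objectives in SAP section 2, and pruritus and GI complaints are the AEs of special interest in Protocol 8.5. Protocol 2.2.2 lists pruritus and constipation among the Study G events with at least twice the placebo incidence, so a doubling is a realistic signal for this drug. The bar plots are also the only exposure-safety output to which SAP 4.8 commits for these events.

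**Working it through.** **Group sizes.** SAP Table 2's figure reproduces: 142 / 2 = 71 per arm under 1:1 allocation. The 142 itself follows from Protocol 9.1: 96 / (0.75 × 0.90) = 142.2. Allowing for the 10% lead-in drop-out in Protocol 9.1, 142 × 0.90 = 127.8 subjects are randomized, about 64 per arm.

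| Per arm | Per tertile | Per quartile | Placebo / drug group |
|---|---|---|---|
| 71 | 23.7 | 17.75 | 3 or 4 |
| 64 | 21.3 | 16 | 3 or 4 |

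The ratio does not depend on which arm size is used.

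**Expected bar heights.** With N per arm, k exposure groups, placebo risk p and relative risk RR, the expected placebo bar is N × p and the expected drug bar is (N/k) × RR × p. Their ratio is RR/k; p cancels. At RR = 2 the drug bar is 2/3 (tertiles) or 1/2 (quartiles) of the placebo bar. The bars are level in expectation only at RR = 3 or RR = 4.

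**How often the plot misleads.** The documents give no placebo AE rate, so p is assumed at 2%, 5%, 10% and 20%. Let the placebo count be X ~ Bin(64, p) and each drug count be Y ~ Bin(g, 2p), with g = 16 (quartiles) or 21 (tertiles), all independent. Then

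P(all k drug bars strictly below placebo) = Σₓ P(X = x) × [P(Y ≤ x − 1)]ᵏ.

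Results with the risk truly doubled in every exposure group:

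| Assumed p | Expected placebo bar | Expected drug bar, quartile / tertile | P(a given drug bar is lower), quartile / tertile | P(all drug bars are lower), quartile / tertile |
|---|---|---|---|---|
| 2% | 1.3 | 0.6 / 0.9 | 0.52 / 0.47 | 0.28 / 0.27 |
| 5% | 3.2 | 1.6 / 2.1 | 0.70 / 0.60 | 0.45 / 0.38 |
| 10% | 6.4 | 3.2 / 4.3 | 0.83 / 0.71 | 0.64 / 0.51 |
| 20% | 12.8 | 6.4 / 8.5 | 0.95 / 0.84 | 0.87 / 0.71 |

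For the opposite error, set the drug risk equal to placebo at 10%. All four quartile bars then fall below placebo with probability 0.88, which gives a false appearance of protection.

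**With proportions.** At RR = 2 the expected drug bar is twice the placebo bar for any k, for example 20% against 10%.

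**The case against.** The strongest reply is that the drug-versus-placebo AE comparison is already planned with denominators. Protocol 9.5 gives percentages by treatment group, and an excess of pruritus or GI events on drug would be visible there. This stands. A reader might infer from the count plot that the trial's safety reading would hide or reverse a real excess; the documents do not support that. Protocol 9.5 does not, however, give rates by exposure group, so it does not repair this figure.

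Second, the exposure gradient is read mainly across the drug quantiles, which are about equal in size. This also stands: those bars are comparable with each other. A reader who summed them would still see the doubling (12.8 against 6.4 events at an assumed 10% placebo rate and 64 per arm).

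Third, it is tempting to say that a doubled risk will look like fewer events than placebo. That is true of the expected bar heights, not of every realised plot. At assumed placebo rates of 5% or below, all drug bars fall below placebo in fewer than half of trials. Low rates are plausible for overall GI disorders, which SAP 4.8 counts only at grade 3 or higher.

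Fourth, the plot is exploratory, no decision rule is attached to it, and the optional logistic regression would use denominators. This limits the consequence. It does not justify a count axis, and a misleading plot could itself suggest that no model is needed.

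Finally, SAP 4.8 does not forbid printing group sizes, and a stacked display that included subjects without the AE would show each total. But the section specifies a number of subjects, and SAP 4.2 step 8 does not settle which display is meant.

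**Conclusion.** The point holds, as a minor one. As written, the plot sets drug and placebo bars on scales that differ by a factor of 3 or 4. The factor follows from 1:1 allocation, quantile groups of about equal size and an undivided placebo category; it needs no assumption about AE rates. Under a doubled risk, the chance that every drug bar lies below placebo runs from about 0.27 to 0.87. That range rests on assumed placebo rates of 2% to 20%, about 64 subjects per arm and the same relative risk in each exposure group. The effect is confined to the placebo reference in an exploratory figure and does not extend to comparisons among drug quantiles or to the treatment-group AE tables.

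**What to change.** In SAP 4.8, change the plotted quantity from the number to the proportion of subjects with an AE, shown as n/N with an exact 95% CI, for each exposure group and for placebo, and print N under each bar. Use the same description in step 8 of SAP 4.2, so that the two sections define one display. The cost is a small wording edit and a change of axis; no new data are needed.

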#### **4.9. Model Evaluation/Qualification**

Model evaluation/qualification assesses the extent of any mismatch between the model and the data that it is describing. The exact procedures employed depend on the data and models and can therefore not be prescribed.

The following plots may be examined to assess model evaluation/qualification:

- Plots with predicted versus observed values of the response variable(s);
- Plots with predicted values superimposed on plots of the data;
- Various plots of residuals;
- Plots of random effects versus covariates;
- Visual or/and numerical predictive checks (VPC or/and NPC);
- Other plots may be examined as required.

##### **4.9.1. Statistical Considerations in Case of Model Update**

The principle of parsimony will be applied, meaning that the simplest model that adequately fulfils the analysis objective will be preferred. The statistical criteria described below will be used to compare different candidate models by NONMEM:

- To accommodate for multiple comparisons testing, inherent in population PK model development, a 6 points reduction of the objective function value for one additional parameter (either structural or random) in nested models, theoretically coinciding with  $P \leq 0.01$  in a Chi-square ( $\chi^2$ ) test, will be deemed significant during model development.
- For non-nested models, the appropriate Akaike's Information Criterion (AIC) or alternative model selection criteria such as the Bayesian Information Criterion (BIC) may be used.

The statistical criteria outlined below will be used for model assessment

- The standard error of a structural parameter estimates reported by NONMEM should preferably be less than 50% of the estimated parameter value. This would imply that zero is excluded from the 95% CI of the parameter estimate, assuming normality.
- The correlation between parameter estimates (structural and stochastic) reported by NONMEM in the correlation matrix of the model output, should lie between -0.95 and 0.95
- The values estimated for  $\eta$  should be adequately centered around zero (reported p-value in the NONMEM output file should be larger than 0.05).
- Shrinkage of the random effects should preferably be below 30% ( $\eta$ -shrinkage and  $\epsilon$ -shrinkage).

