- Numerical Predictive Check (NPC). The NPC will be performed on the mean and the standard deviation (SD) of the exposure metrics ( $AUC_{24h}$  and  $C_{0h}$ ), since these reflect the central tendency and the variability of the exposure metrics. Within each replicate, the mean and SD of the exposure metrics to be used in the ER analysis will be computed. The model-based distribution of the mean and SD of the exposure metrics across replicates will be obtained and its 2.5th and 97.5th percentile will be used to calculate the lower and upper limit of the 95% confidence interval (CI) of the model-based predicted mean and SD of the exposure metrics, which will be then compared to the actual metric of exposure obtained from the Study 67953964MDD2001. Based on the parameter estimates of the previously developed model, 1000 replicates of the analysis dataset will be simulated.

Adequacy of the model will be assessed by the ability of the model to capture the central tendency and the variability of the data (as attested by the VPC/pcVPC plots) and to provide population and individual predictions without significant bias (confirmed by the GoF plots).

If the external evaluation is unsuccessful, potential refinements of the preliminary population PK model (e.g. modifications of the model structure, re-estimation of population parameters, addition of study-specific factors, etc) will be evaluated in order to adequately describe the data from Study 67953964MDD2001 and the three Phase 1 studies, LAF-A, LAF-B and LAF-C. If a model update is performed, the criteria described in Section 4.9 may be used to compare different candidate models.

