#### 4.4.4. Refining the Covariance Structure

Correlation between PK parameters may be tested after all significant fixed covariate effects have been included in the model. The individual ETAs will be examined graphically by plotting each ETA against all others. If visual inspection of plots reveals any correlation, the corresponding block may be introduced into the OMEGA matrix to test its significance using the likelihood ratio test. If implementing a correlation significantly improves the fit, the block will be kept in the model. The process will be repeated until no further improvement of the fit can be achieved. A model with a full block of correlations between random effects will be used as a reference to determine the maximum possible improvement by optimizing covariance structure.

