In case of  $C_{0h}$ , observed pre-dose exposure may be used as an alternative to the model-estimated  $C_{0h}$ .

The drug effect sub-model may be parametrized as a linear, or if the exposure range allows,  $E_{max}$ , sigmoid  $E_{max}$ , or exponential function, as determined by model building criteria (Section 4.9). In case a delay in onset of drug effect will be observed during the exploratory analysis, the delay will be fit using an appropriate delay function, such as a sigmoid. Additional functional forms of the drug effect sub-models may be tested. Baseline MADRS or SHAPS will be tested as covariate on both drug-related and drug-non-related response in order to assess the potential influence of higher/lower baseline disease severity on MADRS and SHAPS change. Gender, race, and age at baseline will also be tested. Lead-in placebo response will be tested as covariate on models based on the full dataset for change from baseline MADRS scores. Lead-in placebo response will not be tested as covariate for change from baseline SHAPS models, as no effect was observed on SHAPS during the lead-in period based on blinded data. Additional parameter-covariate relationships may be tested if required.

Primary analysis on MADRS will be performed on the enriched population (lead-in non-responders). In case no effect on MADRS is found, change from baseline SHAPS total scores will be analyzed on the full dataset. If appropriate, the analysis on MADRS may be repeated on the full dataset, where both lead-in placebo response as well as baseline SHAPS total score will be tested as covariate in the model.

Change from baseline MADRS or SHAPS total scores obtained during the withdrawal period (Day 78) may be explored and included in the model as function of exposure if deemed appropriate.

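### The 6-point objective-function cut in SAP 4.9.1 gives P of about 0.014 for an added unconstrained parameter, not the stated P≤0.01, which needs a drop of 6.635

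*SAP*

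**What the plan says.** SAP Section 4.9.1 sets the numerical rule for comparing candidate models in NONMEM. It opens with the reason for the rule: "To accommodate for multiple comparisons testing, inherent in population PK model development". The threshold is "a 6 points reduction of the objective function value for one additional parameter"; its full scope reads "for one additional parameter (either structural or random) in nested models", and it is described as "theoretically coinciding with $P \leq 0.01$ in a Chi-square" test. Non-nested models are handled differently: "For non-nested models, the appropriate Akaike's Information Criterion (AIC) or alternative model selection criteria".

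Two other sections point to these criteria. On the population PK model, Section 4.4.1 says: "If a model update is performed, the criteria described in Section 4.9 may be used to compare different candidate models". Section 4.6 lists linear, Emax, sigmoid Emax and exponential forms for the drug effect on MADRS or SHAPS, the choice being made "as determined by model building criteria (Section 4.9"). Apart from Section 4.9.1, Section 4.9 offers only plots and predictive checks, so the only numerical comparison rule it contains is the one in 4.9.1.

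**The concern.** The sentence gives a decision threshold and the significance level that it is meant to deliver, and the two can be checked against each other. For one added parameter the 1% point of chi-square on 1 degree of freedom lies above 6, so the cut is looser than its label for an ordinary parameter. The direction matters because the rule is presented as protection against multiple comparisons. A structural or drug-effect term that lowers the objective function by between 6 and 6.635 would be accepted and reported as meeting P≤0.01 when it does not.

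**Working it through.** **Inputs, all from SAP 4.9.1.** Required drop: 6 points. Degrees of freedom: 1 (one additional parameter). Stated level: P≤0.01, chi-square test. One assumption is needed: the objective function is minus twice the log-likelihood up to a constant. The SAP does not say so, but its chi-square reference requires it.

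**Step 1: try to reproduce the stated level.** On 1 degree of freedom,

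P(χ²₁ ≥ 6) = 2 × [1 − Φ(√6)] = 2 × [1 − Φ(2.449)] = 0.0143.

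The stated P≤0.01 is not reproduced. The difference is 0.0143 − 0.0100 = 0.0043, or 0.43 percentage points; the ratio is 0.0143/0.0100 = 1.43.

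**Step 2: find the cut that gives the stated level.** The 1% critical value is (2.576)² = 6.635. Because the SAP states an upper bound, rounding matters:

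| Drop | P on χ²₁ |
|---|---|
| 6 | 0.01431 |
| 6.63 | 0.01003 |
| 6.635 | 0.01000 |
| 6.64 | 0.00997 |

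To two decimals, 6.64 meets the bound and 6.63 just misses it.

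**Step 3: the random-parameter case.** The same cut is applied to random parameters. A single variance tested at zero lies on the edge of its range, and its reference distribution is a 50:50 mixture of chi-square on 0 and 1 degrees of freedom:

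P = 0.5 × 0.01431 = 0.00715.

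This is below 0.01, so the stated bound holds and the cut is conservative for that test.

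**Step 4: where the rule applies.**

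- Population PK model: only if it is updated, and then as an option (4.4.1).
- Drug-effect form: through 4.6, but only for nested pairs that differ by one parameter, such as adding a linear slope or moving from Emax to sigmoid Emax.
- PK covariate selection: not governed by this cut. Section 4.4.3 gives its own levels: 0.001 for screening, 0.01 for forward selection and 0.001 for backward elimination.
- Non-nested comparisons: AIC or BIC, with no p-value.

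**The case against.** The best defence is that the word theoretically signals an approximation, and that 0.0143 rounds to 0.01 at two decimals. This does not rescue the sentence, because it states an upper bound and 0.0143 exceeds it.

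The other objections concern reach and weight, and they largely stand. The drop in objective function is one criterion among several: the same section asks for parsimony, acceptable standard errors, limited parameter correlations and low shrinkage. Use is conditional. The PK model is refined only if external evaluation fails, and the exposure-response modelling goes ahead only if exploratory plots show a relationship (4.2 and 4.6). The exposure-response objectives are exploratory.

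A reader might infer three stronger things that the documents do not support.

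- **That all candidate models are accepted at a 43% higher error rate.** The ratio of 1.43 holds only for an unconstrained parameter in a nested comparison. For a variance tested at zero, P is 0.007 and the stated bound is met.
- **That the covariance refinement in 4.4.4 is equally affected.** That section adds a block "to test its significance using the likelihood ratio test", but it cites neither Section 4.9 nor the 6-point cut. A block of three or more random effects would also add several parameters at once, which a one-parameter rule does not cover.
- **That the excess compounds to a known amount.** For ten independent null tests, the chance of at least one false acceptance would be 1 − (1 − 0.0143)¹⁰ = 13.4%, against 1 − 0.99¹⁰ = 9.6%. The SAP gives no number of comparisons, and successive fits to the same data are not independent, so these figures are illustrative only.

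**Conclusion.** The point holds: the cut and the significance level in SAP 4.9.1 disagree for one added unconstrained parameter. Six points corresponds to P=0.0143, and P≤0.01 needs at least 6.635. For a single variance tested at zero, the statement is true and conservative.

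The consequence is minor. The supported size is 0.43 percentage points in the nominal error rate per nested one-parameter comparison, assuming the usual large-sample likelihood-ratio behaviour. The modelling is exploratory and conditional. The protocol's primary MMRM comparison (Section 9.2.1) does not use this rule. It still merits correction, because a prespecified threshold should deliver the level printed beside it.

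**What to change.** Make one of two edits in SAP 4.9.1.

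- Replace 6 points with 6.64 (6.635 rounded up) for one additional parameter, keep P≤0.01, and add that this is conservative for a single variance tested at zero, where P would be 0.5 × 0.00997 = 0.0050.
- Keep 6 points and state that it corresponds to P of about 0.014 for one unconstrained parameter.

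The first costs slightly fewer accepted parameters. The second leaves model selection unchanged but states a slightly less favourable P. Neither needs new data or a design change.
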